11.4.3 Analysis of secondary endpoints

11.4.3.1 Analyses of study methodology endpoints

The analysis of study methodology endpoints will be conducted on the ITT population, on the 24-week randomized period, ie, using all available post-baseline data, regardless of IMP discontinuation.

Study methodology endpoints are described in [Section 9.2.1](#).

11.4.3.1.1 Analysis of study methodology questionnaires

For WIWI, WPAI-SP, and OSEP questionnaires a descriptive summary will be provided for each approach group at each applicable visit (baseline and/or Week 24) and, if applicable, change from baseline to Week 24, including:

- WIWI scores for each item
- WPAI-SP: item scores, and combined scores ([Section 9.2.1.2](#))
- OSEP: each item score

For RUQ, descriptive summary will be provided for each approach group at baseline and for each applicable on-treatment visit on the following items:

- Total number of visits (overall and per healthcare professional type)
- Total money spent
- Total time spent

In addition, the total and average resource utilization per patient will be calculated on all on-treatment questionnaires. The change between baseline and this on-treatment average will be calculated.

The change in WPAI-SP and OSEP part 1 (perceptions of diabetes control) scores from baseline to Week 24 will be analyzed using an ANCOVA. This model will include fixed categorical effects of approach group, on randomization strata of screening HbA1c (<7.6%, ≥7.6%) and randomization strata of sites as well as continuous fixed covariates of corresponding baseline score. WIWI and OSEP part 2 scores (measured only at Week 24) will be compared between approach groups using an ANOVA. This model will include fixed categorical effects of approach group, on randomization strata of screening HbA1c (<7.6%, ≥7.6%) and randomization strata of sites.

11.4.3.1.2 Analysis of compliance with IMP

See [Section 11.4.1.1](#).

11.4.3.1.3 Analysis of compliance with key study activities

For the **number of times the patient used the Bluetooth devices** and the **number of times the patient completed blood draw visit** in accordance with the study instructions from baseline to Week 24, only descriptive statistics will be calculated including the number of available data, mean, SD, median, minimum, and maximum. These endpoints will be calculated only for the virtual group.

For **patient withdrawal** from baseline to Week 24, Kaplan-Meier plots/estimates of the cumulative incidence of study discontinuation due to any reason will be provided. Time to study discontinuation is defined as the number of days from Day 1 until the day of study

discontinuation. All completers are considered as censored observations. The censoring time is the number of days from the randomization date until the last visit date.

11.4.3.2 Analyses of diabetes control endpoints

The analysis of diabetes control endpoints will be conducted on the ITT population on the 24-week randomized period, ie, using all available post-baseline data, regardless of IMP discontinuation.

Diabetes control endpoints are described in [Section 9.2.2](#).

11.4.3.2.1 Analysis of diabetes control PROs

For each questionnaire a descriptive summary at each applicable visit (baseline and/or Week 24) and change from baseline to Week 24 will be provided, including:

- DTSQs and DTSQc subscale scores (total treatment satisfaction, perceived frequency of hyperglycemia, and perceived frequency of hypoglycemia, see [Section 9.2.2.1](#))
- HFS-II total score and subscale scores (HFS-B and HFS-W)
- DDS: total score, subscales scores, distress category for total and subscales ([Section 9.2.2.1](#))

The change in DTSQs, HFS-II, and DDS scores from baseline to Week 24 will be analyzed using an ANCOVA. This model will include fixed categorical effects of approach group, on randomization strata of screening HbA1c (<7.6%, ≥7.6%) and randomization strata of sites as well as continuous fixed covariates of corresponding baseline score.

Average scores at Week 24 in total treatment satisfaction score, hyperglycemia perception, and hypoglycemia perception score from DTSQc will be analyzed using an ANCOVA model. This model will include fixed categorical effects of approach group, on randomization strata of screening HbA1c (<7.6%, ≥7.6%) and randomization strata of sites as well as continuous fixed covariates of corresponding baseline score from DTSQs.

11.4.3.2.2 Analysis of glycemetic endpoints

The following endpoints will be analyzed using available data during the 24-week treatment period. A mixed effect model with repeated measures (MMRM) approach will be used, under the missing at random framework carried out via SAS PROC MIXED using an adequate contrast at Visit 12 (Week 24).

This model will be run with an unstructured correlation matrix to model the within-patient errors. Parameters will be estimated using restricted maximum likelihood method with the Newton Raphson algorithm. Denominator degrees of freedom will be estimated using Satterthwaite's approximation. This model will provide baseline adjusted least squares means estimates at Week 24 for both approach groups, as well as the differences of these estimates, with their corresponding standard errors and 95% CIs.

- HbA1c (%): change from baseline to Week 16
- FPG: change from baseline to Week 16 and Week 24
- Change in 7-point SMPG profiles per time-point from baseline to Week 16 and Week 24

For HbA1c endpoint, the model will include fixed categorical effects of trial approach group, visit, trial approach-by-visit interaction, randomization stratum of sites, as well as, the continuous fixed covariates of baseline HbA1c value and baseline HbA1c value-by-visit interaction.

For FPG and 7-Point SMPG endpoints, the model will include fixed categorical effects of trial approach group, visit, trial approach-by-visit interaction, randomization stratum of sites, randomization stratum of HbA1c (7.6 % and $\geq 7.6\%$), the continuous fixed covariates of the corresponding baseline value, and baseline value-by-visit interaction.

11.4.3.3 Analyses of patient care endpoints

The analysis of patient care endpoints will be conducted on the ITT population on the 24-week randomized period, ie, using all available post-baseline data, regardless of IMP discontinuation

Patient care endpoints are described in [Section 9.2.3](#).

11.4.3.3.1 Analysis of investigator questionnaires

For OSES ([Section 9.2.3.1](#)) a descriptive summary will be provided for each approach group at each applicable visit.

For OSES part 1 (study-specific resource requirements), a descriptive summary will be provided for each approach group at each applicable visit, and a total time will be calculated for each patient and averaged within each approach group. Overall Study Experience-Sites part 1 scores will be compared between approach groups using an ANCOVA. This model will include fixed categorical effects of approach group, on randomization strata of screening HbA1c ($<7.6\%$, $\geq 7.6\%$) and randomization strata of sites as well as continuous fixed covariates of corresponding baseline score.

For OSES part 2 (relationship and satisfaction), a descriptive summary will be provided for each item for each approach group at Week 24. Item scores will be compared between approach groups using an ANOVA. This model will include fixed categorical effects of approach group, on randomization strata of screening HbA1c ($<7.6\%$, $\geq 7.6\%$) and randomization strata of sites.

11.4.3.3.2 Analysis of patient interviews

Exit interviews with a subset of patient from the virtual group is described in [Section 9.2.3.2](#). Data will be analyzed via an expert qualitative research analysis group using standardized qualitative methods (eg, thematic analysis, grounded theory). A specific Statistical Analysis Plan and report will be developed for the exit interviews.

11.4.3.4 Analyses of safety endpoints

Safety endpoints are described in [Section 9.2.4](#).

The summary of safety results will be presented by approach group.

All safety analyses will be performed on the safety population, on the on-treatment period, defined as the time from first IMP injection up to 2 days after the last IMP injection.

The baseline value for safety endpoints will be the last available value prior to the first injection of IMP.

11.4.3.4.1 Hypoglycemia

The number and incidence of patients experiencing at least 1 hypoglycemic event will be presented per trial approach group and type of hypoglycemic event ([Section 9.2.4.4](#)) according to time of occurrence (nocturnal [ie, 00:00 to 05:59, by sleep status], any time of the day) during the treatment period. The Odds Ratio and its corresponding 95% CI of virtual group over traditional group for each hypoglycemic event will be estimated by a logistic regression model adjusted on randomization strata of screening HbA1c (<7.6%, ≥7.6%) and randomization strata of sites. This model will also estimate the Odds Ratio of virtual group and traditional group and its corresponding 95% CI.

The number and rate of hypoglycemic events (in patient-year of exposure) will be determined per trial approach group and type of hypoglycemic event ([Section 9.2.4.4](#)), according to time of occurrence (nocturnal [ie, 00:00 to 05:59, by sleep status], any time of the day) during the on-treatment period. For each hypoglycemic event, the rate ratio, and its corresponding 95% CI, of virtual group over traditional group will be estimated using an over-dispersed Poisson regression model adjusted on randomization strata of screening HbA1c (<7.6%, ≥7.6%) and randomization strata of site.

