7.2.2 Exclusion criteria related to the current knowledge of Sanofi compound

- E 17. Known hypersensitivity/intolerance to insulin glargine, rapid-acting insulin analogs, or any of their excipients
- E 18. Patients experienced with any severe hypoglycemic episode resulting in seizure, unconsciousness, or coma, and/or leading to hospitalization during the past 6 months before screening
- E 19. Documented (within 12 months) medical history of unstable proliferative diabetic retinopathy or or macular edema likely to require laser, surgical treatment during the study period
- E 20. Pregnant or breast-feeding women or women who intend to become pregnant during the study period
- E 21. Woman of child-bearing potential (WOCBP) not protected by highly-effective method(s) of birth control and/or who are unwilling or unable to be tested for pregnancy (see contraceptive guidance in [Appendix A](#)).
- E 22. Any country-related specific regulation that would prevent the subject from entering the study

Note: A patient should not be randomized more than once. One time re-screening is allowed at the Investigator's medical judgment for any manageable reasons that cause the screening failure and the patient is likely to be eligible before the enrolment completion.

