2.4.5.1 Analyses of hypoglycemia

All analyses of hypoglycemia events will be performed on the safety population, separately on events occurring during the 24-Weeks TEAE period (as defined in [Section 2.1.4](#)). The analyses planned to be done during the 24-Weeks TEAE period only (as defined in [Section 2.1.4.1](#)).

Patients with at least one hypoglycemia event

- Number and incidence of patients with at least one hypoglycemia event will be presented for any hypoglycemia and for each hypoglycemia ADA category, overall and by time of the day (as described in [Section 2.1.4.1](#)).
- For any hypoglycemia and for each hypoglycemia ADA category (except probable, pseudo), incidence of patients with at least one hypoglycemia will be compared, overall and by time of the day. Odds Ratio and its corresponding 95% CI of Virtual group over Traditional group for each hypoglycemic event will be estimated by a logistic regression model adjusted on randomization strata of screening HbA1c (<7.6%, ≥7.6%) and randomization strata of sites.
- Percentage (%) of patients with at least one severe hypoglycemia event will be summarized by symptom during 24 weeks TEAE period,

Number and rate of hypoglycemia event

- Number and rate of hypoglycemia event per patient-year will be summarized for any hypoglycemia and for each hypoglycemia ADA category (as described in [Section 2.1.4.1](#)), overall and by time of the day (as described in [Section 2.1.4.1](#)). Non classified hypoglycemia will be displayed.
- For any hypoglycemia and for each hypoglycemia ADA category (except probable, pseudo), the number of hypoglycemia events per patient-year will be compared, overall and by time of the day. For each hypoglycemic event, the rate ratio, and its corresponding 95% CI, of Virtual group over Traditional group will be estimated using an over-dispersed Poisson regression model adjusted on randomization strata of screening HbA1c (<7.6%, ≥7.6%) and randomization strata of sites.

For Hypoglycemic ADA categories, only the threshold hypoglycemia episodes with plasma glucose ≤70 mg/dL (3.9 mmol/L) will be analyzed.

Subgroups analyses

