- The incidence of patients with at least one any hypoglycemia during the 24-week TEAE period, will also be presented by the following subgroups (defined below) and analyzed using a similar logistic regression model approach as presented previously, but adding the corresponding subgroup factor and study conduct approach arm-by-subgroup interaction factor. Odds ratio estimates and 95% CI will be provided in each subgroup category. The interaction study conduct approach arm-by-subgroup p-value will be provided for descriptive propose. When the subgroup considered is equal to one of the randomization strata or is part of one of the adjustment factor, this randomization stratum/adjustment factor is removed from the model. If the logistic regression model does not converge (eg, due to sparse data) some of the randomization strata may be removed. Forest plots will be

provided. Further subgroup analyses may be performed if deemed necessary for interpretation of results.

- Age group (<65, [65-75[and ≥ 75 years),
- Gender (male, female),
- Baseline BMI (<25, [25-30[, [30-40[and ≥ 40 kg/m²),
- Randomization stratum of screening HbA1c (<7.6%, $\geq 7.6\%$),
- Randomization stratum of site. (only if the size of subgroup is relevant)
- Duration of diabetes (<10, ≥ 10 years),
- Baseline estimated GFR categories (mL/min/1.73m²): (<60[; ≥ 60),

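### For sparse hypoglycemia categories such as severe and nocturnal severe, the odds ratio as designed has no finite value when one arm has no event, and no risk difference with a confidence interval is planned beside it

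*Protocol*

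**What the plan says.** **Odds ratio.** Protocol 11.4.3.4.1 plans, for each type, an odds ratio of virtual over traditional with a 95% CI, which "for each hypoglycemic event will be estimated by a logistic regression model adjusted on randomization strata of screening HbA1c" and for site. The types are broken down "according to time of occurrence (nocturnal [ie, 00:00 to 05:59, by sleep status], any time of the day"; nocturnal severe hypoglycemia is therefore one of the modelled outcomes. The next sentence adds: "This model will also estimate the Odds Ratio of virtual group and traditional group and its corresponding 95% CI". This names the same quantity again.

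**SAP version.** SAP 2.4.5.1 uses the same model, for the day as a whole and split into night and daytime, but narrows the list: "For any hypoglycemia and for each hypoglycemia ADA category (except probable, pseudo), incidence of patients with at least one hypoglycemia will be compared". Severe hypoglycemia stays in. Neither document names an exact or penalized method or a minimum number of events.

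**Sparse data.** One rule exists, in the subgroup bullet of SAP 2.4.5.1: "If the logistic regression model does not converge (eg, due to sparse data) some of the randomization strata may be removed".

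**Other measures.** Incidence per group is planned: "Number and incidence of patients with at least one hypoglycemia event will be presented for any hypoglycemia" and for each ADA category. Event rates per patient-year are also planned, with a rate ratio "estimated using an over-dispersed Poisson regression model" with the same adjustment. Neither document plans a difference in incidence with a confidence interval.

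**After termination.** SAP section 2 records that the trial was stopped with 15 patients randomized instead of 150, and that only basic descriptive statistics will be provided.

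**The concern.** Both groups take the same insulin. The approaches differ in whether titration is supervised remotely or with site visits, so severe hypoglycemia is a central safety contrast. It is also likely to be among the sparser categories: follow-up is 24 weeks, there are at most 75 patients per arm, and E 18 excludes "Patients experienced with any severe hypoglycemic episode resulting in seizure, unconsciousness, or coma" and/or leading to hospitalization in the six months before screening.

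Neither document names another estimation method, so the model is read as ordinary maximum likelihood. If one arm then has no event, the software prints an extreme odds ratio with a huge standard error, or a convergence warning, and the Wald interval means nothing. The table would have no usable effect estimate in a category where a reader would look for one, although the same data support a finite estimate.

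**Working it through.** **Plan's own figure.** The documents state no incidence, precision or power for hypoglycemia, so there is nothing to reproduce. The stated precision of 0.37% concerns HbA1c and does not bear on this point.

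**Inputs.**
- 75 patients per arm (Protocol 11.1).
- Site and HbA1c stratum as covariates (Protocol 11.4.3.4.1, SAP 2.4.5.1).
- At least 3 sites (Protocol 6.1) or about 6 (SAP 1.1), with no pooling (SAP 2.5.6).
- 24-week risk of at least one event per patient, p: **assumed**, from 0.5% to 5%, equal in both arms.

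**Step 1: why an empty arm breaks the model.** With an intercept and an approach term, maximum likelihood makes the fitted probabilities in each arm add up to the number of patients with an event in that arm. If that number is zero, every fitted probability in the arm is driven to zero and the log odds ratio diverges. This holds with or without site and HbA1c terms, so removing strata does not help. The Poisson model has the same property for event counts, so the rate ratio fails with it.

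**Step 2: how often an arm is empty.** P(at least one arm empty) = 1 − [1 − (1 − p)^75]^2.

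| Assumed p | (1 − p)^75 | P(at least one empty arm) | Expected patients with an event, 150 × p |
|---|---|---|---|
| 0.5% | 0.687 | 90% | 0.75 |
| 1% | 0.471 | 72% | 1.5 |
| 2% | 0.220 | 39% | 3.0 |
| 3% | 0.102 | 19% | 4.5 |
| 5% | 0.021 | 4% | 7.5 |

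The probability passes one half at p of about 1.6%: setting it to 0.5 gives (1 − p)^75 = 0.293.

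**Step 3: with the planned covariates.** In a simulation of the additive model (800 trials per setting, equal sites, HbA1c strata split 50/50), the approach odds ratio had no finite estimate at risks of 1%, 2%, 3% and 5% in 69%, 43%, 19% and 4.5% of trials with 3 sites, and in 73%, 43%, 19% and 3.5% with 6 sites. This agrees with Step 2: the empty arm drives the failure.

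**Step 4: the opposite extreme.** If every patient in an arm has an event, the odds ratio diverges in the same way. With 75 per arm, that happens in at least one arm in 4% of trials at an assumed risk of 95%, and in 39% at 98%. Very common categories can therefore fail too.

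**Step 5: what the alternatives return.** Illustrative counts, virtual 0/75 and traditional 3/75:
- Maximum likelihood: (0 × 72)/(75 × 3) = 0. The fit stops at a log odds ratio near −29 with a standard error near 900,000.
- Firth, unadjusted: half an event added to each cell gives (0.5 × 72.5)/(75.5 × 3.5) = 0.14, profile-likelihood 95% CI 0.001 to 1.45. With the planned covariates it is 0.14 (3 sites) or 0.15 (6 sites).
- Incidence difference: 0% − 4.0% = −4.0 points, Miettinen-Nurminen 95% CI −11.1 to 1.0.

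**The case against.** The strongest objection is that SAP section 2 has set these models aside. After termination at 15 patients, only tables and listings are due. A reader might infer that the study report will contain odds ratios that cannot be estimated; the current SAP does not support that. This stands, and it confines the point to the method as designed. At the actual size the restriction is sensible: with 15 patients and 6 sites, the simulated odds ratio is non-finite in 96% of runs at 5% risk and 84% at 10%.

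Other stronger readings also fail:
- *Every hypoglycemia type is affected.* The protocol models each type, but the SAP leaves out probable and pseudo.
- *Failure is to be expected.* That depends on a risk the documents do not give. E 18 does not settle it, because the analysed severe category covers any event needing another person's active assistance, which is wider than the episodes that E 18 excludes.
- *Sites without events ruin the comparison.* They do not. With 6 sites and 5% risk, some site or HbA1c coefficient is non-finite in 87% of simulated trials, but the approach odds ratio fails in only 3.5%.
- *There is no absolute information.* Counts, percentages and patient-year rates per group are planned, so the crude difference can be read off. Only an interval for it is missing.

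It can also be said that this is an unpowered, descriptive pilot and that a Firth interval from 0.001 to 1.45 decides nothing. That is fair about precision. But a wide, valid interval describes the data, whereas a diverged estimate does not.

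Finally, a generous reader could extend the strata-removal rule to the main model. By Step 1 that would still not help.

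**Conclusion.** The point holds for the analysis as designed for 150 patients. In sparse categories, notably severe and nocturnal severe, the planned odds ratio has no finite value when an arm is empty. The rate ratio shares the fault, and the SAP's convergence rule does not repair it.

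The size depends on an assumed risk, equal in both arms. At about 2% or below, failure is a substantial possibility (39% or more). At 3% it is 19%, and at 5% or above it is uncommon (4% or less). No claim is made about which of these risks applies.

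The gap in absolute measures is narrower: the group figures are planned, but an incidence difference with an interval is not. The protocol's second odds-ratio sentence is redundant at any incidence. The current report is not affected, given SAP section 2. The point matters because Protocol section 4 presents this pilot as preceding full-scale studies, where the same text could be reused.

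**What to change.** In Protocol 11.4.3.4.1 and SAP 2.4.5.1, or in the template for follow-on studies if these documents are no longer to be amended:

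1. Estimate the odds ratios by Firth penalized likelihood, with profile-likelihood 95% CIs and the same covariates.
2. Replace the protocol's second odds-ratio sentence with the incidence difference, virtual minus traditional, and a Miettinen-Nurminen 95% CI. Add the same line to the SAP.
3. State that when an arm has no events, the rate ratio is reported as not estimable and the rates per group are shown.

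The cost is one option in PROC LOGISTIC, one column in the incidence tables and one sentence for the rate ratio. The downside is small: Firth estimates are pulled slightly towards 1 when events are few.

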11.4.3.4.2 Adverse events

All AEs will be coded to a preferred term (PT), high level group term (HLGT), high level term (HLT), and associated primary system organ class (SOC) using the version of medical dictionary for regulatory activities (MedDRA) currently in use by the sponsor at the time of database lock.

Adverse event incidence tables will present by SOC (sorted by internationally agreed order), HLGT, HLT, and PT sorted in alphabetical order, and for each approach group, the number (n) and percentage (%) of patients experiencing at least one AE. Multiple occurrences of the same event in the same patient will be counted only once in the tables within a treatment period. The denominator for computation of percentages is the safety population within approach group.

Adverse event incidence table will be provided by study conduct approach group for all types of TEAEs: all TEAEs, all treatment emergent SAEs, all TEAEs leading to permanent treatment discontinuation and all TEAEs related to local tolerability at injection site and hypersensitivity.

Death

The following deaths summaries will be generated on the safety population:

- Number (%) of patients who died by study period (TEAE, on-study, poststudy) and reasons for death summarized by allocated approach group
- Death in nonrandomized patients or randomized and not treated patients
- TEAE leading to death by primary SOC, HLGT, HLT and PT showing number (%) of patients sorted by internationally agreed order of SOC and alphabetic order of HLGT, HLT, and PT

Post-study deaths, if presented, will follow safety guideline instruction.

Injection site reaction and hypersensitivity reaction

Number (%) of patients with events related to injection site reactions or hypersensitivity reaction will be provided separately.

Adverse event of special interest

A listing of patients with symptomatic overdose with IMP/NIMP will be provided separately.

Patients with an SAE or AESI should be followed until resolution, stabilization, or death as appropriate.

Product technical complain

Information regarding PTC will be described.

